6.13.2 Performing Adverse Events Assessments or Recording of Adverse Events

The Study Center staff will record and monitor all AEs throughout the Analysis Phase of the study (1-year post-intervention), from the time of transplanted lung reperfusion until the end of the subject's study participation. At all study visits, reports of AEs will be elicited by a verbal probe ("How are you feeling?"). Subjects will be encouraged to contact the Study Center to report an AE at any time. Appropriate measures, including medical intervention and/or procedures, will be instituted if clinically indicated at the discretion of the Investigator.

All AEs occurring during the study must be documented, and any AEs occurring during the first 90 days post-transplant must be reported in the CRFs for AEs. For each AE, the Investigator will evaluate the severity and seriousness, as well as the relationship of the AE to the device and procedure. Information relating to the AE, such as onset and cessation date and times, seriousness, severity, relationship to device/procedure, action taken, and outcome will also be documented in the subject's source documentation for assessment. Where possible, AEs should be recorded using standard medical terminology. If several signs or symptoms are clearly related to a medically defined diagnosis or syndrome, the diagnosis or syndrome should be recorded, not the individual signs and symptoms.

6.13.3 Timing of Adverse Event Collection

All AEs are collected from the time of transplanted lung reperfusion through subject participation duration (1 year post-operative). Reporting procedures are described in Section 6.13.7.

Subjects with AEs that are ongoing at the subject's last Study Center visit must be followed until resolution or for 30 days after the subject's last Study Center visit, whichever comes first. Adverse events that are recorded during the 7 days following the subject's last Study Center visit will be followed until resolution or for up to the 30 days after the subject's last Study Center visit, whichever comes first. All AEs that are ongoing after follow-up for 30 days' time will be recorded as ongoing. The Investigator is expected to provide or arrange appropriate supportive care for any subject with ongoing AE(s).

Serious adverse events (SAEs) should be followed until they resolve or the event or their sequelae stabilize. Supplemental measurements and/or evaluations may be necessary to investigate fully the nature and/or causality of an AE or SAE. Such supplementary assessments may include additional laboratory tests, diagnostic procedures, or consultation with other healthcare professionals. The subject's source documents and CRFs for AEs should be updated with any new or additional information as appropriate.

If the subject reports or the Investigator learns of any new SAE that occurs up to 30 days after the subject's last clinical site visit, the clinical site personnel will ensure that these data are reported on the AE CRF.

6.13.4 Severity

The Investigator will use the following scale to grade the severity of any AEs:

- Mild: no intervention required; no impact on activities of daily living (ADL)
- Moderate: minimal, local, or non-invasive intervention indicated; moderate impact on ADL
- Severe: significant symptoms requiring invasive intervention; subject seeks medical attention, needs major assistance with ADL

6.13.5 Relationship

The relationship of an AE to EVLP procedure and lung transplant must be assessed by the Investigator using the following guidelines:

- **Related:** The event is associated with the use of the investigational device or with procedures beyond a reasonable doubt
- **Possibly Related:** The relationship with the use of the investigational device or procedure is weak but cannot be ruled out completely; alternative causes are also possible.
- **Unlikely:** The relationship with the use of the investigational device or procedure seems not relevant and/or the event can be reasonably explained by another cause, but additional information may be obtained.
- **Not related:** There is no temporal relationship between the investigational device or procedure and the event onset, an alternate etiology has been established.

6.13.6 Expectedness

The Sponsor, Independent Medical Monitor, and the Study Principal Investigator will be responsible for determining whether an SAE is expected or unexpected. An AE will be considered unexpected if the nature, severity, or frequency of the event is not consistent with the risk information previously described for the intervention. Anticipated adverse events not related to EVLP as listed in Section 6.13.1 are for purposes of this study considered to be “expected” events and do not require AE reporting.

6.13.7 Reporting Procedures

The Sponsor will report all AE’s occurring during the first 90 days post-transplant, and all SAEs occurring during the one-year Analysis Phase of the study to the FDA in the annual Investigational Device Exemption (IDE) report. Each reported AE will include date of onset, actions taken, severity, seriousness of the event, relationship of the event to the EVLP procedure or lung transplant, and the outcome of the event.

6.13.7.1 Reporting Serious Adverse Events

All SAEs, including subject deaths, are reported to the CRO within one working day after awareness via the Adverse Event CRF. The Sponsor shall review all SAEs to assess if related or anticipated. Any event that meets the serious criteria, is unanticipated, and related to the device system is reviewed by the Sponsor Independent Medical Monitor and subject to expedited reporting to FDA and participating IRBs in accordance with the Unanticipated Adverse Device Effect requirements (21 CFR 812.150). The Sponsor or Sponsor’s representative will report any

results of an evaluation of UADE to the FDA, Institutional Review Board (IRB), and all Investigators within 10 business days following receipt of notice of the event(s).

All other SAEs for the Analysis Phase of the study will be reported to FDA in the annual IDE report.

In addition to the above, it is the responsibility of the Study Investigator to abide by the AE reporting requirements stipulated by the IRB.

6.13.7.2 Reporting Procedure for Serious Adverse Events

Any AE meeting the specified SAE criteria will be submitted on an AE CRF to the CRO. This report may be sent by fax or email. Once submitted, the CRO will send a confirmation email to the Investigator within one business day. The Investigator should contact the CRO if this confirmation is not received. This process applies to both initial and follow-up SAE reports.

SAE Reporting Contact Information:

Safety Fax Line (US): [name]

Product Safety Email: [contact]

General questions about SAE reporting can be directed to the Safety Help Line (available 8:00AM – 5:00PM Eastern Time): **[name]**

The Study Investigator will complete an AE CRF with fax cover sheet found in the study manual and submit via fax or email within the following timelines:

- All SAEs, including deaths, regardless of relationship, will be reported by fax or email within 24 hrs of site awareness.
- All SAEs will be followed until resolution or stabilization.

6.13.8 Initial Safety Review

The Sponsor will temporarily pause the study after the twentieth (#20) subject has been enrolled to allow time for the FDA to review safety data on the first 10 EVLP subjects and any control subjects enrolled who have reached 90-days post-transplant.

Data from the first 10 subjects through their 90-day visit will be submitted to FDA as an IDE Supplement for review. Submitted data will include graft survival, aggregate PGD scores, FEV₁, oxygen required at rest, and BOS Grade. The study will be on hold during this review with the exception of Subjects 11 through 20 who are “ongoing”; these subjects will continue to come to the Study Center as specified in the protocol. Upon satisfactory review, the FDA will permit the continuation of the study to the full subject enrollment. If the FDA has concerns, the Sponsor will address these in a satisfactory manner.

6.13.9 Halting Rules

The Sponsor shall implement an immediate enrollment pause if there is any of the following:

- a third subject death within the first 30 days post- transplant;
- if the PGD3 rate at T72 $\geq 50\%$ in the first 10 subjects; or
- the Medical Monitor shall review all UADEs and deaths in the study and will make a determination if an unreasonable risk to subjects exist. If an unreasonable risk has been determined based on the opinion of the Medical Monitor, the trial, or the parts that cause the risk, shall be stopped until an alternate solution can be devised by the Sponsor and accepted by each IRB and FDA.

6.14 Removal of Subjects from the Study

Subjects may withdraw voluntarily from the study or the Investigator may terminate a subject's participation. Withdrawing from the study will not affect subject's status/ability to receive a standard lung transplant.

Subjects are free to withdraw from participation in the study at any time upon request.

The Investigator may withdraw a subject from the study for any reason, including but not limited to, the following:

- Any clinical AE, laboratory abnormality, or other medical condition or situation occurs such that continued participation in the study would not be in the best interest of the subject.
- The subject meets an exclusion criterion (either newly-developed or not previously recognized) that precludes further study participation.
- A protocol violation occurs.
- The Sponsor or Investigator terminates the study.

It is unlikely that a subject will discontinue study participation after receiving a lung transplant, as a lifetime of required follow-up, immunosuppression monitoring, and infection control is required after transplantation to minimize the chance of graft failure and/or death. Every effort will be made to undertake protocol-specified safety follow-up procedures to capture AEs, SAEs, and UADEs.

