1.2.1 Potential Risks

The specific additional risks associated with EVLP beyond those encountered in lung transplant generally include extending ischemia beyond the initial cold ischemic period, increased potential for contamination due to additional handling and manipulation of the lungs, and potential lung damage that might result from the perfusion process and associated procedures, such as cannulation, bronchoscopy, and repackaging, among others. Specific risks and mitigation strategies are addressed in [Appendix 3](#).

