EVLP lungs that exceed 10 hrs of CIT-1, or are perfused for less than 3 hrs or more than 6 hrs will be discarded by the Sponsor according to the responsible OPO's directions.

First lung CIT-2 is the elapsed time between the end of the EVLP procedure and removal of the first lung from cold storage, marking the beginning of the implantation phase of the transplant procedure. This CIT-2 may not exceed 6 hrs. Prior to shipping EVLP lungs to the Study Center, an estimated time of arrival at the Study Center will be calculated by the EVLP Specialist in

consultation with the Study Center to ensure the criterion for CIT-2 will be met. Therefore, if the anticipated first lung CIT-2 will exceed 6 hrs due to logistical considerations (projected flight time and/or surgical staff schedule, etc.), the lungs shall not be transported to the Study Center. Similarly, if after leaving the EVLP facility, prolonged transport time or patient logistical or other issues compromise the ability to ensure actual first lung CIT-2 is less than 6 hours, the transplant shall not proceed.

The implantation phase of the transplant procedure begins upon removal of the first lung from cold storage, marking the end of CIT-2. The warm ischemic time (WIT) period then begins, which lasts until the lung is reperfused in the recipient. This time period is expected to be no longer than the typical WIT at each Study Center for standard lung transplants.

For DLT procedures, the second lung must remain in cold storage in low potassium dextran solution while the first lung implantation is being performed. The time of removal of the second lung from cold storage after the first lung is implanted and the second lung WIT should be consistent with historical surgical experience for sequential DLT at each Study Center. However, if the time between the start of CIT-2 and removal of the second lung from cold storage exceeds 10 hrs, a protocol deviation shall be documented on a CRF and shall be reported to the Sponsor. The reason for the delay and an assessment of the second lung's condition prior to transplant shall be recorded in the CRF. These subjects will continue enrollment in the study and will be followed in the EVLP Group.

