4.3 Exclusion Criteria

Patients who meet any of the following criteria will be excluded from the study:

1. Patients listed for same-side lung re-transplantation.
2. Patients listed for multiple-organ transplantation including lung and any other organ.
3. Patients listed for live donor lobar transplant.
4. Patients positive for human immunodeficiency virus (HIV), active Hepatitis B or C, or *Burkholderia cepacia* infection.

5. Patients in the ICU at the time of the initial lung offer requiring ventilation, ECMO or ECLS. [Note: The decision to place the recipient on ECMO or other ECLS for post-transplant prophylaxis at time of or immediately prior to transplant is not considered an exclusion]
6. Patient receives a conventional (non-EVLP) lung transplant but does not match to an EVLP subject based on the criteria for control matching outlined in Section 3.1.

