7.5 Early Termination Procedures

As lung transplant requires life-long follow-up care from the transplant center, it is unlikely a subject will withdraw from this study post-transplant. Subjects may withdraw consent to participate prior to receiving the intervention (lung transplant) within this study without consequence to the subject or study. In the event that a patient withdraws consent after lung transplant, the following data will be collected by the Study Center either through OPTN and/or SRTR reports or via an early termination visit:

- Subject and graft survival and if failed, cause of failure
- FEV₁
- Oxygen required at rest
- BOS Grade
- Physical capacity
- Working for income status
- Hospital readmission date/s (if applicable)
- Assess AEs

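### Protocol 6.14 lets an investigator withdraw a transplanted subject on outcome-related grounds, and nothing requires outcome follow-up to continue afterwards

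*Protocol*

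**What the plan says.** Protocol 6.14 gives an open-ended power: "The Investigator may withdraw a subject from the study for any reason, including but not limited to, the following". Three of the listed grounds matter here.

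- **Adverse event or medical condition:** "Any clinical AE, laboratory abnormality, or other medical condition or situation occurs such that continued participation in the study would not be in the best". The quotation stops just before the clause ends; a judgement about what serves the subject is a condition of this ground.
- **Exclusion criterion:** "The subject meets an exclusion criterion (either newly-developed or not previously recognized) that precludes further study participation". The criterion must preclude further participation.
- **Protocol violation:** "A protocol violation occurs". This ground carries no condition.

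Protocol 5.3 and 10.4.2 place enrolment at transplantation. The recipient exclusions in 4.3 include "Patients listed for same-side lung re-transplantation" and infection with HIV, active hepatitis B or C, or *B. cepacia*.

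On data after discontinuation, Protocol 7.5 begins: "In the event that a patient withdraws consent after lung transplant, the following data will be collected by the Study Center". Table 3 has a single premature-discontinuation column. Section 6.14 promises best efforts to capture AEs, SAEs and UADEs.

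The SAP analyses all enrolled subjects (4.2). It codes a missing T72 grade as PGD3 and leaves missing 30-day vital status and other missing safety data as missing (4.4, 6.1).

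**The concern.** The intervention is a single transplant that cannot be undone, and it is complete when a patient becomes an enrolled subject. No study treatment is left to stop, so withdrawing that subject can end only data collection.

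Some of the grounds overlap with what the study measures. Relisting for same-side re-transplantation can follow graft failure, and graft survival is an endpoint. A new infection can meet the infection exclusion, and Protocol 1.2.1 names "increased potential for contamination due to additional handling and manipulation of the lungs" among the risks specific to EVLP. An adverse event is itself a safety outcome.

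If subjects who are doing badly are withdrawn more often, and their later status is not collected, the remaining data look safer than they should. Investigators are unblinded (Protocol 5.4), so the effect could differ between EVLP and Control. It would also carry into the Control estimates intended for designing future studies (Protocol 9.2).

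**Working it through.** **Planned figures.** No planned figure addresses removal. The sample size supplies only the denominator, and it reproduces: n0 = 1.645² × 0.10 × 0.90 / 0.06² = 67.64. With the finite-population correction, 67.64 / (1 + 66.64/2057) = 65.52, rounded up to 66. One subject is 1/66 = 1.5 percentage points.

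**Is a withdrawn, transplanted subject still followed?**

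| Section | What it secures | Limit |
|---|---|---|
| Protocol 6.14, closing sentence | Best-effort capture of AEs, SAEs, UADEs | Graft status, BOS and FEV1 not named |
| Protocol 6.13.2, 6.13.3 | AE recording; new SAEs to 30 days after the last visit | Recording ends with participation; later SAEs only if learned of |
| Protocol 6.13.7 | Deaths reported as SAEs | Needs site awareness |
| Protocol 7.5 | Survival, graft status, FEV1, BOS and more, from registry reports or one visit | Triggered by consent withdrawal only |
| Protocol 6.5, 6.7, 6.9 to 6.11, Table 3 | An assessment at premature termination | One time point |
| Protocol 10.5 | 6- and 12-month OPTN/SRTR recipient reports requested | 10.11.2.3 takes Analysis Phase data from site CRFs; no stated use to fill gaps |
| Protocol 6.16 | Survival to be documented for all subjects | No mechanism for withdrawn subjects |

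No row requires scheduled outcome follow-up through Year 1 after withdrawal by the investigator.

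**Which endpoints are exposed?** All counts below are assumptions chosen to show direction and scale.

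- *PGD3 at T72.* Missing counts as failure, so the error runs against the device. With 7 observed events (7/66 = 10.6%), 1 to 3 further missing values give 8/66 = 12.1% to 10/66 = 15.2%.
- *30-day mortality.* Missing is dropped. Suppose 3 of 66 die: 4.5% (exact 95% CI 0.9% to 12.7%). If 1 of the 3 was withdrawn and vital status lost, the report is 2/65 = 3.1% (0.4% to 10.7%). If 2 were, it is 1/64 = 1.6% (0.04% to 8.4%). With 2 observed deaths and 1 to 3 unknown, the possible rate runs from 2/66 = 3.0% up to 3/66 = 4.5%, 4/66 = 6.1% or 5/66 = 7.6%.
- *One-year survival.* Suppose 10 of 66 die, so true survival is 56/66 = 84.8%. If k of the 10 were withdrawn first and their deaths never captured:

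| k | Survival, missing dropped | Deaths, denominator 66 |
|---|---|---|
| 0 | 56/66 = 84.8% | 10/66 = 15.2% |
| 1 | 56/65 = 86.2% | 9/66 = 13.6% |
| 2 | 56/64 = 87.5% | 8/66 = 12.1% |
| 4 | 56/62 = 90.3% | 6/66 = 9.1% |

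SAP 6.3 asks for number and percentage per category and does not say whether missing subjects stay in the denominator. With 66 retained, the proportion alive stays correct but deaths are undercounted.

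**The case against.** The strongest reply is that 6.14 is loosely worded boilerplate and other provisions catch most of the data. Several parts of this stand.

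- **Qualifiers.** A reader might infer that any AE permits removal. The text does not say so: the AE ground needs a best-interest judgement, and the exclusion ground needs a criterion that precludes participation. Only the protocol-violation ground is unconditional.
- **Pre-transplant scope.** Section 6.14 says withdrawal does not affect access to a standard transplant, and consent may precede transplant by a year, so part of it reads as pre-transplant. But the list has no time limit, and the section goes on to discuss discontinuation after transplant. SAP 7.2.5 plans a table of intervention-emergent AEs leading to withdrawal, so post-transplant removal is contemplated.
- **The triggering event is usually recorded.** A reader might infer that the graft failure or infection itself disappears. Failure date and cause are collected, and the infection would be an AE or SAE. What is at risk is what happens next.
- **Visibility.** SAP 5.1 tabulates withdrawal reasons by group, so uneven removal would show. That reveals the loss but does not recover the data.
- **Conflict with 3.1.1.4.** For a second-lung CIT-2 deviation, that section says: "These subjects will continue enrollment in the study and will be followed in the EVLP Group". A reader might call this a flat contradiction. It is a specific rule beside a permissive one and the two can be read together, though they sit uneasily and should be reconciled.
- **Uneven rule between groups.** A reader might infer bias because exclusion 6 (no match) applies only to Controls. Matching depends on transplant type and diagnosis group, so it does not arise from a post-transplant outcome. The exclusion for ventilation or ECMO is likewise tied to the initial lung offer.

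**Conclusion.** The point holds as a gap in the follow-up rule. An investigator may withdraw a transplanted subject on grounds that overlap with safety outcomes, and no section requires scheduled outcome follow-up after that. Section 6.16's statement that survival will be documented for all subjects has no mechanism behind it for these subjects.

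The main exposure is descriptive, exploratory and safety data from Day 90 to Year 1: survival, graft status, BOS, FEV1 and AEs or SAEs after removal. The likely direction is favourable, assuming withdrawn subjects fare worse than the rest. The size cannot be stated, because the documents give no removal rate and expect discontinuation to be unlikely.

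A reader might infer that the co-primary results are biased towards safety. The documents do not support that. PGD3 at T72 moves the other way under failure coding, and 30-day mortality is affected only if vital status is lost despite SAE reporting and the registry. This is an inexpensive correction worth making; it does not show that material bias will occur.

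**What to change.** **Protocol 6.14.** State that withdrawal of a transplanted subject by the investigator does not end outcome follow-up, which ends only with withdrawal of consent, loss to follow-up, death or study termination. State that protocol violations, and exclusion criteria newly met after transplant, are recorded as deviations or AEs and are not grounds to stop follow-up. The investigator's best-interest discretion over study visits and procedures can remain.

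**Protocol 7.5.** Replace the consent-withdrawal trigger with discontinuation for any reason. State that vital and graft status, with dates, through Year 1 will be taken from the OPTN/SRTR reports already requested under 10.5, as consent permits, and used in the analysis.

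**Cost.** A wording amendment with no new visits or procedures, since recipients stay in lifelong transplant care. The downside is that sites will follow a few subjects they might otherwise have dropped.

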6.15 Premature Termination or Suspension of the Study

This study may be suspended or prematurely terminated if there is sufficient reasonable cause. Written notification, documenting the reason for study suspension or termination, will be provided by the suspending or terminating party to Study Investigators, the IDE Sponsor, and all regulatory authorities. If the study is prematurely terminated or suspended, the Principal Investigator will promptly inform the IRB and will provide the reason(s) for the termination or suspension.

Circumstances that may warrant termination include, but are not limited to:

- Determination of unexpected, significant, or unacceptable risk to subjects.
- Insufficient adherence to protocol requirements.
- Data that are not sufficiently complete and/or evaluable.
- Determination of futility.

